## 1.0 Study Summary

Study Title	Pathophysiology of Aerodigestive Reflex in Infants: GERD Management Trial
Study Design	Single center randomized control trial
Primary Objective	To compare two feeding approaches and their effect on clinical outcomes in infants with proven Gastroesophageal Reflux Disease (GERD)
Secondary Objective(s)	To determine the pathophysiological mechanism of success or failure to either therapy, we will test the hypothesis and validate results from the preliminary data by utilizing our diagnostic tools to identify differences between the two study arms in regards to: aerodigestive reflexes, esophageal clearance mechanisms, neuromotor markers of swallowing, and pH-Impedance-symptom indices.
Research Intervention(s)/ Investigational Agent(s)	Both groups will have esophageal manometry studies followed by randomization into two groups, Conventional and Study. The conventional group allows for unrestricted feeding volumes with no time limit, feeds given in any position and random post prandial feeding positions. The study group will have permissive feeding volume restrictions, feeding duration of at least 30 minutes, feeding given in right side lying, and supine post prandial position. Both groups will be treated with omeprazole per NCH NICU guidelines

IND/IDE #	N/A
Study Population	Infants admitted to the NICU at NCH and referred to the Neonatal and Infant Feeding Disorders program for evaluation of Gastroesophageal reflux Disease (GERD)
Sample Size	120
Study Duration for individual participants	5 weeks
Study Specific Abbreviations/ Definitions	GMT (GERD Management and Therapy Trial) RSL- right side lying ARI –Acid reflux index PMA= (Gestational age at birth + chronologic age)

## 2.0 Objectives

### 2.1 Purpose, specific aims or objectives

- Clinical trial based on objective evaluation of symptoms scored by blinded independent rater during pH-Impedance studies (Aim 1).
- Investigates the neuro-physiological aspects of the reflexes involved with GERD and its complications (Aim 2).
- Unique to this proposal, we will apply physiologically rational, and safe, therapeutic strategies that have the real potential to ameliorate GERD symptoms/complications. If the proposed aims are achieved, we anticipate:
  - Finding that not only acid, but also feeding volume, position and maturational changes in adaptation underlie the pathogenesis of GERD, and in this way clearly identifying relevant new therapeutic targets for this disease.
  - Understanding the various stimulus-targets and provoked reflexes that lead to sensitization of afferents, and thereby symptoms associated with GERD.
  - Understanding the mechanism(s) underlying functional esophageal disorders in infants, thereby clarifying the pathophysiology of symptoms presumed to be GERD related.
  - Development of cost effective, efficacious methods for the diagnosis and management of GERD in infants.
  - Establishing objective criteria for evaluating the need for anti-reflux surgical procedures in infants.

### 2.2 Hypothesis

- Aim 1
  - The innovative feeding strategy provided over 4 wks is more effective than standard therapy for the acquisition of safe feeding skills by improved symptom scores (Primary), improved individual I-GERQ-R measures, growth measures, reduced lengths of stay and resource utilization (Secondary).
- Aim 2
  - The sensory-motor characteristics of aerodigestive reflexes evoked with induced esophageal stimulation or upon spontaneous esophageal provocation as in GER, improve in the innovative therapy group with regards to: sensory thresholds, response latency and duration, frequency and magnitude of reflexes, TLESRs, spatial-temporal-physical- chemical characteristics of GER events with associated symptom indices.

## 3.0 Background

### 3.1 Relevant prior experience and gaps in knowledge

- The NASPGHAN-2009 guidelines define GERD as reflux of gastric contents in the presence of troublesome symptoms and/or complications. The prevalence of GERD in premature infants is estimated to be 10.6 %. Premature infants have pathologic reflux with esophageal manifestations (e.g. irritability, feeding refusal, arching, dysphagia) and extra- esophageal manifestations (e.g. arousals, cardiorespiratory-, sensory-, and physical symptoms, chronic lung disease, impaired growth). Such high risk infants suffer chronic morbidity, longer hospitalizations, re- admissions, and account for an unacceptable health care burden.
- Current treatment approaches in infants are likely to fail because of lack of clear therapeutic targets. Furthermore, GERD symptoms are non-specific and heterogeneous such that designing effective approaches to symptom based management is very difficult.
- Exact economic burden of premature infant GERD is lacking. 12.7% (525,000) out of 4,131,019 births in 2009 were born at < 37 wks. Assuming that half (263,000) of these infants are in NICUs, and given our estimated prevalence of GERD as 10.6% (27,900) and the estimated cost per admission attributable to GERD was \$76,796; we project an estimated economic burden attributable to GERD as over \$2.1 billion. Others have estimated that 48% of ICU discharges are treated for presumed GERD. Clinical significance of GERD is also evident from the 7-fold increase in the use of acid suppressive medications, and indeed about 45% of anti-reflux procedures are performed in infants (15). These numbers ignore the quality of life issues for both the patients and the parents.
- Extensive developments with the mechanisms, physiology, pharmacotherapy and clinical approach to GERD in the human adult, as well as therapeutic limitations in infants are well recognized. Specifically for infants, there are no available safe or FDA-approved prokinetics that regulate esophageal motility and suppress transient lower esophageal sphincter (LES) relaxations.

### 3.2 Relevant Preliminary Data

- In an observational study in infants (N=35) referred for GERD management, we studied the impact of feeding methods (volumes, duration, flow rates, caloric density, osmolality) on pH-Impedance variables of GER. The conclusions were: longer feeding duration, less feeding volume, and slower flow rate led to less total GER events, fewer nonacid GER events and shorter bolus clearance time; whereas, caloric density and osmolality of feeds has no impact on the characteristics of GER.
- The effect of right lateral position on accelerated gastric emptying has been described by others (107, 108, 114), and the effect of supine posture in the prevention of ALTEs or SIDS is recognized in the AAP guidelines.
  - 2003 Apnea, sudden infant death syndrome, and home monitoring. Pediatrics 111:914-917.
- We used state-of-the-art methods including, multimodal esophageal sensory provocation concurrent with video, pH-Impedance and symptom indices in the investigation of sensory-motor aspects (sensory thresholds, reflex frequency, response latency, duration and magnitude) of Vago-vagal reflexes (Primary and Secondary Peristalsis, Upper esophageal sphincter contractile reflex-UESCR, Lower esophageal sphincter relaxation reflex-LESRR and Pharyngeal reflexive swallowing) that facilitate swallowing and esophageal clearance to maintain airway protection in neonates. Twelve pharyngo esophageal motility studies were done in 6 subjects, 3 in each group, at inception (test-1) and again at completion of therapy (test-2). With innovative strategy, the response onset to esophageal stimulation induced LESRR is decreased at T2 in addition to a greater LES relaxation magnitude compared to T1; in contrast, response onset to LESRR and LESRR magnitude are similar at T1 and T2 for standard therapy. This finding supports the hypothesis that LES relaxation governed by inhibitory vagal effects mediated by nitrergic neurons is rapidly restored with innovative feeding strategy, similar to those changes tested during maturation.
- Clinical outcomes from 44 subjects that had reflux index >3% were measured; 24 infants had lower feeding volumes, longer feeding duration, greater compliance to supine postprandial posture (innovative feeding strategy); 20 infants had standard feeding

therapy, all received acid suppressive therapy. This trial supported the hypothesis that the innovative feeding strategy is superior to standard feeding therapy.

### 3.3 Statistical procedures

- Statistical Analyses:
  - Aim I: Outcomes: We will test the hypothesis that the innovative feeding strategy provided over 4 wks is more effective than standard therapy for the acquisition of safe feeding skills by improved symptom scores (Primary), improved individual I-GERQ-R measures, growth measures, reduced lengths of stay and resource utilization (Secondary). Linear mixed models will be used to study the associations between the primary endpoints for Aim 1 (symptom scores) and treatment, and trend across time. The interaction term “group x time” will be included in the model to study whether the two treatment groups have different “behavior” across time. Confounder variables, such as medications, feeding position or volume, will be included in the models. Logistic regression models will be used to assess success of the treatment vs. standard of care. Also, potential confounders (e.g. feeding method: oral vs. tube) will be included and studied in these models. Holm’s method will be used to adjust for multiple comparisons (150). All the secondary variables listed above, will be analyzed using either linear mixed models or logistic regression models. Model goodness of fit tests and residual analyses will be performed to assess the models. Interaction terms and potential confounder variables will be included.
  - Aim II: Mechanistic Hypothesis: We will test the hypothesis that the sensory-motor characteristics of aerodigestive reflexes evoked with induced esophageal stimulation or upon spontaneous esophageal provocation as in GER, improve in the innovative therapy group with regards to: sensory thresholds, response latency and duration, frequency and magnitude of reflexes, TLESRs, spatial-temporal-physical- chemical characteristics of GER events with associated symptom indices. Based on the preliminary data, we will have at least 80% power to detect the above differences of pre and post therapy between the two groups. Linear mixed models or logistic regression models (depending on the nature of the outcome variable) will be used to study the associations of interest within sensory motor components of aerodigestive reflexes within and between study groups and their outcomes. Potential confounders as well as interaction between groups and type of infusion will be included in the models. We have utilized similar models previously. Correlation between symptom indices (SI, SSI, SAP) and reflexes will be calculated.
- Sample Size Determination:
  - From the more recent preliminary data analysis, 83.3% (20/24, 95% CI: 62.6%-95.2%) of patients had success based on symptoms and feeding methods in the innovative strategy group, while only 35% (7/20, 95% CI: 15.4%-59.2%) had success in the standard therapy group. In order to provide greater assurance than afforded by comparing to historical control of the standard therapy, a total of evaluable 100 patients will be randomized into the innovative feeding strategy or standard therapy group. The chi- square test yields 80% power to detect 27% or higher increase in proportion of success while maintaining an overall one-sided  $\alpha$  level of 0.025. This conservative power calculation is supported by the preliminary data and assumes the proportion of success for the standard therapy is around 40% and a group-sequential design with O’Brien-Fleming error spending function.
- Interim Analysis:

- One interim futility analysis will be undertaken at about 50% information prior to the final analysis at 100% information, corresponding to 50 and 100 evaluable patients, respectively. The boundary is determined using Lan-DeMets spending functions to simulate O'Brien-Fleming boundaries with an overall one-sided  $\alpha$  level of 0.025. Using the target proportion of success, the boundary at the futility analysis expressed as a p-value is 0.297. We plan to enroll 120 patients to allow for 20% of attrition.
- Intention to treat analysis:
  - Every patient who had been randomized will be included in the analysis. If a patient drops off before end of study and no symptom score has been measured, we will treat the patient as a failure. Beside the intention to treat analysis, we will also perform the analysis with only those patients that complete the study. Linear mixed models will be used to study the associations between the primary endpoints for Aim 1 (symptom scores) and treatment, and trend across time. The interaction term “group x time” will be included in the model to study whether the two treatment groups have different “behavior” across time. Confounder variables, such as medications, feeding position or volume, will be included in the models. Logistic regression models will be used to assess success of the treatment vs. standard of care. Also, potential confounders (e.g. feeding method: oral vs. tube) will be included and studied in these models. Holm's method will be used to adjust for multiple comparisons. All the secondary variables listed above, will be analyzed using either linear mixed models or logistic regression models. Model goodness of fit tests and residual analyses will be performed to assess the models. Interaction terms and potential confounder variables will be included.
  - The proposed projects will focus on esophageal provoking stimuli in designing multi-faceted innovative therapies, that will be studied in a prospective single center randomized blinded controlled trial. The pH- Impedance data with associated symptom indices will be analyzed. This trial will advance our knowledge of GER and GERD in infants. These studies will likely mandate the development of infant-specific diagnostic and treatment paradigms to manage not only GERD but also other diseases where GERD is a co-morbidity.

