## STUDY OUTCOMES

### Primary and Secondary Clinical Outcomes

The clinically meaningful primary and secondary outcomes did not differ significantly between groups (**Table 2**). I-GERQ-R scores for study and conventional groups are shown (**Fig 2**). At inception: positive I-GERQ-R was 19/35 (54%) in the conventional group vs 24/37 (65%) in the study group,  $p=0.36$ . At Time-2: positive I-GERQ-R prevalence was 9/31 (29%) in the conventional group vs 13/34 (38%) in the study group,  $p=0.43$ . In the study group vs conventional group, respectively: a) primary outcome achieved in 33% (95% CI, 19% - 49%) vs 44% (95% CI, 28% - 62%) ( $p=0.28$ ), b) secondary outcomes: independent oral feeding in 65% (95% CI, 48% - 80%) vs 77% (95% CI, 60% - 90%),  $p=0.26$ ,  $\geq 6$ -point I-GERQ-R decrease in 38% (95% CI, 22% - 56%) vs 35% (95% CI, 19% - 55%),  $p=0.82$ , length of stay was 98 [81-132] days vs 108 [83-125] days,  $p=0.89$ , and oxygen requirement at discharge in 19% (95% CI, 8% - 35%) vs 26% (95% CI, 13% - 43%),  $p=0.49$ . There were no significant differences in growth metrics (all  $p>0.05$ ) or developmental scores at 2 years (all  $p>0.05$ ). Feeding outcomes or I-GERQ-R scores did not significantly differ between conventional vs study groups based on feeding method at inception (**Table 3**). Individual I-GERQ-R questions relating to vomiting, regurgitation, and crying (i.e. frequency of emesis, volume of emesis, symptoms with emesis, and crying more than usual in the

past week) had no differences ( $P>0.05$ ) within the group or between the groups across maturation for these individual symptoms, except for symptoms with emesis (never: rarely: sometimes: often: always, %) was 16:16:42:19:6 for conventional group at Time-1 vs 18:18:29:0:35 for study group at Time-1,  $p < 0.01$ .

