## 4.0 Study Endpoints

- Primary Outcome
  - **Clinical outcome of feeding success for those infants transitioning to oral feeds at inception.**
    - The primary endpoint is the feeding success defined as achieving full oral feeds (defined as no need for tube feeds to maintain hydration and nutrition) and/or a  $>/=$  6-point decrease from baseline I-GERQ-R. The time frame is up to 5 weeks after enrollment.
  - **Clinical outcome of feeding success for those infants on full oral feeds at inception.**
    - The primary endpoint is the feeding success defined as maintaining full oral feeds and a  $>/=$  6-point decrease from baseline I-GERQ-R. The time frame is up to 5 weeks after enrollment.
- Secondary Outcomes
  - Clinical Outcomes
    - Length of hospital stay
    - Growth outcomes during the study period and up to 1 year
    - Independent feeding skills over time up to 1 year
    - Respiratory support during the study period and at discharge
    - Developmental outcomes with Bayley's scores at 2 years
    - Individual differences in I-GERQ-R questionnaire
  - Motility Outcomes
    - Mechanisms of aerodigestive clearance and esophageal provocation are evaluated based on esophageal motility studies at inception and after 5 weeks.
  - pH Impedance outcomes
    - 24-hour pH impedance results at inception of study and then 5 weeks later after treatment completed

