## **6.0 Procedures Involved\***

### **6.1 Study design:**

- Study design and setting: This is a Single Center Prospective Randomized, Blinded Controlled Trial. Consented subjects will undergo 1:1 randomization into either innovative feeding strategy and standard therapy arms.
- Patient Population: Potential study subjects are those that are referred by their attending physician for evaluation and management of potential GERD, the key symptoms being irritability and arching, gagging, choking, coughing, aspiration, life threatening events, swallowing problems, and/or failure to thrive. I-GERQ-R questionnaire will be completed as per guidelines. Each patient must have a signed consent from parent/legal guardian prior to initiation of screening for the trial.
- Inclusion Criteria: Hospitalized convalescing infants with aerodigestive symptoms or admitted for GERD symptoms, < 42 weeks GA. Infants will be included if PMA at time of study is  $\geq$  34 wks age and  $\leq$  60 wks. Subjects must be on full enteral feeds defined as  $\geq$  150mL/k/day. Infants must be breathing unaided, and nasal cannula oxygen up to 1 LPM is allowed. In subjects receiving empiric prokinetics or acid suppressive agents, the medications need to be stopped for  $\geq$  72 hr prior to evaluation.
- Exclusion Criteria: Infants with known genetic, metabolic or syndromic disease, neurological diseases such as Grade III or IV intra ventricular hemorrhage or perinatal asphyxia, GI malformations and surgical GI conditions.
- Tests and procedures
  - Twenty-four-hour pH and impedance ordered diagnostically for suspected GERD
  - If RI  $>3$  and infant meets all above criteria, infant randomized into conventional or study group
  - Esophageal manometry performed
  - 4 weeks of the study intervention for the study group and standard treatment for the conventional group while collecting data on symptoms, feeding position, duration and volume

- Omeprazole stopped after 4-week course.
- Repeat esophageal manometry and pH impedance testing done after 1 week off omeprazole (at week 5). If the providers/parents are resistant or refuse to stop the medication, repeat testing will still be done, and the alteration will be noted.

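### The symptom-score mixed model makes no stated use of the baseline score, so its group-by-time test is essentially a change comparison; a common baseline mean would be at least as precise in large samples

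*Combined protocol and SAP*

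**What the plan says.** Protocol section 3.3, Aim I, uses linear mixed models to study "associations between the primary endpoints for Aim 1 (symptom scores) and treatment, and trend across time". The group-by-time term "will be included in the model to study whether the two treatment groups have different" courses over time. On covariates it says: "Confounder variables, such as medications, feeding position or volume, will be included in the models". The Intention to treat paragraph of the same section repeats this plan. Neither place names the baseline score as a covariate or says that the arms share a baseline mean. Neither says which coefficient is the treatment effect, or how many readings enter.

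The protocol has no I-GERQ-R visit schedule. Section 6.1 says only "I-GERQ-R questionnaire will be completed as per guidelines". The endpoint in section 4.0 needs one baseline and one later score: a "6-point decrease from baseline I-GERQ-R. The time frame is up to 5 weeks after enrollment". The report gives results at inception and at Time-2: "At Time-2: positive I-GERQ-R prevalence was 9/31 (29%) in the conventional group vs 13/34 (38%) in the study group". The report's section on participant selection says that randomisation was stratified by ARI category (3-7%, >7%) and by preterm or full-term birth. Section 3.3 does not name these factors as covariates.

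**The concern.** When treatment, time and their interaction are all in the model, each arm has its own baseline mean. With two readings, the interaction is then the difference between arms in mean change. Randomisation makes the expected baseline difference zero, so the model spends information on estimating a quantity already known by design.

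What is at stake is the width of the interval for the bundle's effect on the continuous score. The data are already thin: 100 evaluable infants were planned, 76 were randomised, 72 are in the secondary analysis and 65 have a Time-2 score (31 conventional, 34 study). The report's Key Points and Conclusion state that feeding modification has no impact and no role. How far such statements can be supported depends on interval width.

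**Working it through.** **Inputs from the documents.** The model terms are those of protocol section 3.3. The two readings come from section 4.0 and from the report's outcome section. There are 65 Time-2 scores. The documents give no score SD and no Time-1 to Time-2 correlation, so both are assumptions here.

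**The plan's own figure.** The only stated power figure belongs to the binary endpoint: 40% versus 67%, one-sided 0.025, 80% power, 50 per arm. The unpooled normal approximation gives (1.96 + 0.84)² × (0.40 × 0.60 + 0.67 × 0.33) / 0.27² = 49.6, so 50 per arm, with power 80.3%. The pooled form gives 53 per arm, or 78.1% power at 50. The figure is reproduced, and nothing below touches it. No precision figure is given for the symptom-score model.

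**Step 1: what the interaction estimates.** With two complete readings, the free-baseline interaction equals the difference in mean change. In one simulated data set (50 per arm, r = 0.5) the mixed model and the simple change comparison both gave -0.0743 with SE 0.2209. Removing the baseline group term cut the variance by 27%, against 25% expected.

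**Step 2: direction.** Let s1 and s2 be the SDs at Time-1 and Time-2, and c = 1/n1 + 1/n2.

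- Change: variance = c(s1² + s2² - 2·r·s1·s2)
- Baseline adjustment, large samples: variance = c·s2²(1 - r²)
- Difference: c(s1 - r·s2)²

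The difference is never negative, whatever r and the SDs. The direction therefore needs no assumed figure.

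**Step 3: size with equal SDs and no other covariates.** The variance ratio, adjusted over change, is (1 - r²) / [2(1 - r)] = (1 + r)/2.

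| r (assumed) | Variance ratio | Loss in inverse variance | Fall in SE after the fix |
|---|---|---|---|
| 0 | 0.50 | 50% | 29% |
| 0.3 | 0.65 | 35% | 19% |
| 0.5 | 0.75 | 25% | 13% |
| 0.7 | 0.85 | 15% | 8% |
| 0.9 | 0.95 | 5% | 2.5% |

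Simulation (3,000 runs, 50 per arm) gave losses of 35%, 24% and 13% at r = 0.3, 0.5 and 0.7. This checks the algebra and says nothing about the true r. With 65 infants, a change comparison carries about the information of 65 × 0.65 = 42, 65 × 0.75 = 49 or 65 × 0.85 = 55 infants analysed with adjustment.

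**Step 4: unequal SDs.** With k = s2/s1, the loss is 1 - k²(1 - r²)/(1 + k² - 2rk).

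| k (assumed) | r = 0.3 | r = 0.5 | r = 0.7 |
|---|---|---|---|
| 0.8 | 50% | 43% | 37% |
| 1.0 | 35% | 25% | 15% |
| 1.2 | 24% | 13% | 3% |

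**The case against.** **The parameterisation and the number of readings are inferred.** This stands in part. The text is silent on how baseline enters and on the I-GERQ-R schedule. Section 2.1 speaks of symptoms scored during pH-impedance studies, and section 3.3 lists symptom scores apart from individual I-GERQ-R measures. On the other side, the report's Abstract and design section call the I-GERQ-R the symptom score, and the endpoint is built on its change from baseline. If six evenly spaced readings were modelled with a linear slope and equal correlations, the analysis would no longer be a simple change score. The loss would still be similar: 37.5%, 23.4% and 12.5% at r = 0.3, 0.5 and 0.7.

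**The formula is not for the model as planned.** This stands. The planned covariates include feeding position and volume, which are parts of the bundle. Report Table 2 shows median right-side feeding of 5% (conventional) versus 78% (study), and total fluid volume at Time 2 of 143 versus 133. With such covariates in the model, the interaction is not a plain difference in mean change and (1 + r)/2 does not describe its variance. That is a further reason to leave them out.

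**Missing scores.** This stands. With 65 Time-2 scores among 76 randomised infants, the identity with a completers' change score is approximate. ANCOVA and the constrained mixed model are then not the same analysis either.

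**Stronger readings.** A reader might infer that the trial is known to have lost 15-35% of its precision. The documents do not support that, because the figure needs an r of 0.3-0.7 and equal SDs. A reader might also infer that the planned test is biased. It is not: under randomisation a change comparison is valid. Finally, the study arm was more often I-GERQ-R positive at inception (24/37 versus 19/35) and at Time-2 (13/34 versus 9/31), yet slightly more often had a 6-point fall (38% versus 35%). A reader might take this as proof that a change analysis misled the trial. None of these differences is significant, and all are dichotomised, so they prove nothing about the continuous model.

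**Conclusion.** The point holds as an efficiency and specification issue for one analysis. On the ordinary reading, the planned group-by-time test is valid but, in large samples, never more precise than a baseline-adjusted comparison that uses scores already collected. The size is conditional: a 15-35% loss in inverse variance for r of 0.7 down to 0.3 with equal SDs and no other covariates. Over the same r it is 37-50% if the follow-up SD is 0.8 times baseline, and 3-24% if it is 1.2 times.

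It would go too far to say that this undermines the trial's main result. Section 4.0 defines the primary endpoint as binary, section 3.3 powers it by chi-square, and the report tests it by chi-square. The primary comparison, the 100 evaluable infants and the futility boundary are unaffected.

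**What to change.** In section 3.3, in both the Aim I and the Intention to treat text:

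- Name the modelled score and its readings.
- Fit the mixed model with a common Time-1 mean: time and group by post-baseline time, with no baseline group term. This keeps infants without a Time-2 score. The report gives inception status for 72 infants and Time-2 status for 65, so 72 - 65 = 7 would otherwise drop out. The alternative is ANCOVA of Time-2 on Time-1 among infants with both scores.
- Add ARI category and preterm or full-term birth as covariates. Report Table 1 implies only 76 - 68 = 8 full-term infants, so main effects are enough.
- Leave feeding position and volume out of the treatment-effect model, because allocation affects them. They can be reported as compliance measures.
- Report the adjusted between-arm difference with its 95% CI.

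The cost is a few lines of plan text and one model fitted to data already held. The report's Statistical Methods section describes no mixed model for this score, so this may be a new fit. ANCOVA uses one degree of freedom for the baseline score, and each stratification factor uses one more.

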## **5.0 Study Intervention/Investigational Agent**

- Those subjects randomized into the study group will follow innovative feeding strategy for 5 weeks. The innovative feeding strategy is as follows:
  - Feeding Volume  $\leq$ 140 ml/kg/d
  - Feeding duration over 30 minutes
  - Right lateral feeding position
  - Supine position postprandial

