- Overall Study Endpoints: Primary clinical outcome occurs at time 2 study or at discharge if time 2 study not completed. Secondary study outcomes occur at time 2 studies. Secondary clinical outcome measures (growth characteristics, development and long term feeding outcomes) will be collected up to 24 months.
- Methods to overcome potential confounders: Data will be collected from EPIC documentation, feeding diaries, parent interviews and follow up appointments. While inpatient, these are documented regularly. After discharge, we will be dependent on parents to provide the data.
- Removal and management of subject(s) from protocol: The investigator and/or the parent(s) have the right to withdraw from study at any time and opt for the standard of care. Parent(s) that withdraw their infants from the study therapy will be encouraged to continue to remain in the study for all follow up evaluations. Those who choose completely withdrawal from the study will be encouraged to follow the standard of care; wherein, response failures are followed for secondary outcomes until 18 months.
- Secondary Outcome Measures: (up to 24 months, for Bayleys developmental score) Secondary outcome measures (growth characteristics, development and long term feeding outcomes) will be collected up to 12 months.

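### Section 3.3 lets on-treatment volume, position and medication enter the symptom-score model as confounders, so group × time may not estimate the effect of assignment

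*Combined protocol and SAP*

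**What the plan says.** Section 3.3 (Aim I) plans a linear mixed model for symptom scores, which it labels primary for Aim 1, with group × time to show whether the arms behave differently over time. It then states: "Confounder variables, such as medications, feeding position or volume, will be included in the models". The Intention to treat paragraph of 3.3, which keeps every randomised infant, repeats the sentence. Neither place says whether the values are taken before or after randomisation, or how they are coded. Both paragraphs end with "Interaction terms and potential confounder variables will be included". For the logistic models the text is "Also, potential confounders (e.g. feeding method: oral vs. tube) will be included and studied in these models".

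Two of the three named variables belong to the intervention. Of the bundle arm, section 1.0 says it "will have permissive feeding volume restrictions, feeding duration of at least 30 minutes, feeding given in right side lying, and supine post prandial position". Section 5.0 lists a volume limit and "Right lateral feeding position" among the bundle components. Section 6.1 has the 4-week intervention run "while collecting data on symptoms, feeding position, duration and volume", and on data sources it says "Methods to overcome potential confounders: Data will be collected from EPIC documentation, feeding diaries, parent interviews and follow up appointments".

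The third variable, medication, can also change after randomisation. Section 6.1 states: "If the providers/parents are resistant or refuse to stop the medication, repeat testing will still be done, and the alteration will be noted". Revision 4 in the IRB revision history lets practitioners raise the dose.

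**The concern.** A confounder of a randomised comparison would have to precede allocation. Volume and position during treatment are consequences of allocation and are the route by which the bundle is meant to work. If the model holds them fixed, group × time measures only what remains of the bundle's effect once its volume and position parts are removed. That is a different estimand from the one the intention-to-treat heading promises. A null or positive score result could then not be read as the effect of random assignment. Because the coding is unstated, the choice between the two estimands could also be made after the data are seen.

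**Working it through.** **Plan's own figure.** Section 3.3 gives no power for the mixed model. Its 80% is for the chi-square test: 50 per arm, 40% vs 67%, one-sided 0.025. With unpooled variance, SE = √[(0.40×0.60 + 0.67×0.33)/50] = 0.0960; 0.27/0.0960 = 2.81; 2.81 − 1.96 = 0.85, so power is 80.3%. With pooled variance it is 78.1%. The figure reproduces, and this test is unaffected.

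**Which reading is realistic.** A baseline reading is open, but there is little at baseline to adjust for. Section 9.0 restricts entry to 150–170 ml/kg/day, and total intake at inception has IQR 149–154 (Table 1). Table 1 lists no feeding position at inception; Table 2 gives position as a percentage of time. The arms separated by design: Time 2 volume was 143 vs 133 ml/kg/day, and right-side feeding for more than 75% of the time was 0/35 vs 21/37 (conventional vs study, Table 2).

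**What each coding does.** Write the score as y = a + b·g + c·t + d·g·t + γ·V, with t = 0 or 1. Differencing within infant gives Δy = c + d·g + γ·ΔV.

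- If V is constant over time (a baseline value, or an on-treatment summary as a main effect), ΔV = 0 and d is untouched.
- If V varies over time, d = total effect − γ × (arm difference in ΔV). From the Table 2 medians, that difference is (133 − 150) − (143 − 150) = −10 ml/kg/day.
- A summary × time term acts on Δy in the same way.

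Take an assumed total effect of −3 points. If γ = 0.3 per ml/kg/day, d = −3 − (0.3)(−10) = 0. If γ = 0.15, d = −1.5. A simulated fit with 4,000 per arm (assumed score SD 5, within-infant correlation 0.5) gave −2.93 unadjusted and +0.08 with time-varying volume in the first case, and −3.04 and −1.51 in the second. Baseline volume, or Time 2 volume as a main effect, left −2.93 and −3.04 unchanged.

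**Precision cost.** Volume compliance was 9/35 vs 27/37 and right-side feeding 0/35 vs 21/37. Treat the indicators as independent within arm and the arms as equal in size.

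- Arm differences: 0.473 and 0.568. Mean within-arm variances: 0.194 and 0.123.
- D² = 0.473²/0.194 + 0.568²/0.123 ≈ 3.78.
- R² of arm on both = (D²/4)/(1 + D²/4) = 0.486; VIF = 1/(1 − 0.486) = 1.94; SE ratio √1.94 = 1.39 (this applies to summary × time).

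**Illustration at trial size.** Random-intercept model fitted by REML, complete data, 50 per arm, change-score residual SD 1, ICC 0.5, 2,000 replicates. The effect is 0.566 SD, set to give 80% power at one-sided 0.025. The mediated share is split equally between volume and right-side feeding. Entries are for 0 / 50 / 100% mediated.

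| Coding of the two indicators | % of effect kept by group × time | Mean SE | Power |
|---|---|---|---|
| None | 100.4 / 98.8 / 101.1 | 0.199 / 0.202 / 0.209 | 0.799 / 0.777 / 0.767 |
| Summary, main effect only | identical | identical | identical |
| Time-varying | 100.6 / 48.9 / 2.3 | 0.264 / 0.264 / 0.264 | 0.568 / 0.189 / 0.034 |
| Summary × time | 100.5 / 48.7 / 2.2 | 0.282 / 0.283 / 0.282 | 0.518 / 0.164 / 0.032 |

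Main-effect coding is not wholly neutral. It moves the group main effect to 0.009 / −0.140 / −0.287 SD, so an arm contrast at Time 2 (group + group × time) keeps 101.9 / 74.0 / 50.5%.

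**Volume alone.** SD = IQR/1.349 gives 3.7 and 5.2 at inception, and 10.4 and 8.2 at Time 2 (conventional, study). With inception–Time 2 correlation 0.25, time-varying volume keeps 98.3 / 51.1 / 0.4%, with power 0.709 / 0.253 / 0.029 against 0.792 / 0.778 / 0.715 unadjusted.

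**Sensitivity.** At ICC 0.3 and 0.7, time-varying power is 0.593 / 0.187 / 0.040 and 0.546 / 0.191 / 0.029. With Time 2 scores missing at random at the Table 2 rates (31/35 and 34/37 scored), main-effect coding still leaves group × time unchanged.

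**The case against.** The strongest reply is that this is an ambiguity and not a demonstrated error. No section says time-varying, and two of the three codings leave group × time alone. The closing line on interaction terms follows a sentence about secondary variables and may refer only to those. The section 6.1 list of sources describes data capture, starts with the electronic record and names no covariate. Volume, duration and position have another documented use: the report's Study Oversight section calls them compliance measurements. The reported Statistical Methods describe no mixed model, and they already name a treat-as-treated analysis. The retained percentages largely restate the assumed mediated share, and medication was not simulated. Adding the single word baseline would be enough.

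Much of this stands. The closing line and the list of sources are weak evidence of intended coding, and the simulation shows a mechanism, not a forecast. What does not fall is the conditional point. The sentence says these variables will be included, two of them are what was randomised, and their baseline versions carry little or no tabulated information. The change of estimand under time-varying or summary × time coding does not depend on the assumed effect size. A restriction to baseline would cure the estimand problem. Naming the covariates also prevents a later choice among them.

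**Conclusion.** The concern holds as a conditional one and should be fixed. As written, section 3.3 permits a model in which group × time is not the intention-to-treat effect. Under that coding the estimate loses whatever share of the effect passes through volume and position: about half if half is mediated, and nearly all if all is. Even with no mediation, the SE rises by a factor of about 1.1 (volume alone, time-varying), 1.3 (both indicators, time-varying) or 1.4 (summary × time). These sizes rest on an assumed effect, ICC and mediated share, none of which the documents give.

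The reach is limited to the planned Aim 1 symptom-score models. The powered chi-square test and the reported unadjusted primary comparison (16/36 vs 13/40, p = 0.28) are untouched. The logistic term for feeding method most naturally means the value at inception, as in section 4.0 and Table 3, and needs only to say so.

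**What to change.** In both paragraphs of section 3.3, replace the sentence on confounder variables with:

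> Covariates in the Aim 1 between-arm models are limited to variables fixed before randomisation: the stratification factors (ARI 3–7% or >7%; preterm or full term) and feeding method at inception, with baseline I-GERQ-R as the baseline time point. Feeding volume, position, duration and PPI exposure after randomisation are reported as adherence measures, or in a separately labelled mediation or as-treated analysis.

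In the logistic sentence, specify that feeding method is the value at inception. Keep group × time and the other planned interactions, restricted to baseline covariates. The Aim II models are outside this change.

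The cost is wording in two places, plus the added words in the logistic sentence. No new data are needed: the strata, feeding method at inception and baseline I-GERQ-R are already collected. The arm effect adjusted for on-treatment feeding is kept, but as a secondary analysis.
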